11.2. Statistical and Analytical Plans

a. Study Statistical Analysis

Statistical analysis will be performed using STATA version 10.0 for Windows (StataCorp, TX, USA). Descriptive statistics will be used to describe subjects' demographics in each group.

Analysis of UL Functional Outcome

Wilcoxon signed-ranked tests will be used at each time points (pre, 2 weeks after start of intervention, post, 1month post-intervention, 3months post-intervention) to compare UL functional outcomes between the experimental and control groups. The significance level for all statistical tests will be set at $p<0.05$ levels. All data will be analysed by intention to treat.

Analysis of feasibility of accelerometers to measure affected UL use

Analysis of the compliance rate and responses from the questionnaire will be used to determine the feasibility and acceptance of using accelerometers to measure affected UL use after stroke.

Analysis of SURE Program's feasibility

Wilcoxon signed-rank test will also be used to compare outcomes of pain, fatigue and spasticity pre-and post-intervention period. The differences in the duration of affected UL use per day and the ratio of affected UL use/ non-affected UL use between the experimental group and control group (from the accelerometer recordings), the rate of compliance, the proportion of subjects who successfully complete the whole training, and the dropout rate will be calculated to assess the feasibility of **SURE Program**.

Analysis of fMRI investigation

Comparison of activation in primary motor cortex, secondary motor cortex and cerebellar hemisphere for bilateral sides will be done by comparing mean percentage signal change (%SC), absolute voxel counts (VC) and changes in geometric centers of these areas on both sides¹⁷. In addition, a laterality index (LI) will also be calculated to determine the relative cortical activity. Asymmetry has been found to restore to normal (L=1.0) when the affected hand movement improved after rehabilitation⁴¹.

Analysis of resting state fMRI/DTI

Functional connectivity and tract integrity^{32,38} will be studied by FSL with the normalization method^{39,40}. The secondary degeneration of the brain in the remote region to the primary lesion will also be studied for the sub-groups of subjects with less motor recovery³⁰.

MRS analysis

A one-way ANOVA test will be performed to assess differences across the visits (pre, post, and 3months post intervention). Provided a significant difference is found, a paired t-test will be used. Due to an abundance of measurable metabolites, metabolite analysis will be limited to those defined by our hypothesis (changes in GABA and Glx) to minimise multiple comparisons.

b. Safety Analysis

Safety analysis will be done by monitoring the adverse events and complaints of the study daily.

c. Interim Analysis

Interim analysis of the data and study's safety and complaints will be performed every quarterly. If the analysis of study's safety shows that the subjects' safety is compromised because of the study procedures, the study will stop.

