3.5. Withdrawal Criteria

Subject will be withdrawn from the study if the subject is unable to tolerate the SURE program

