5. STUDY DESIGN

Experimental procedure

The subjects will be randomly assigned to a control (N=10) and experimental group (N=10).

Experimental Group

The experimental group will receive one **SURE** program booklet with specific instructions and pictorial illustrations of each exercise and functional use according to their affected ULFM score. There are 3 booklets available (Level 1A for patients with affected ULFM score from 0 to 10; Level 1B for patients with affected

ULFM score from 11 to 22; Level 2 for patients with affected ULM score from 23 to 50). Each **SURE** program booklet consists of stretching exercises, strengthening exercises and performance of simple motor tasks such as reaching, picking up cubes etc. Each exercise will be graded and progressed according to the subjects' affected UL capability by the Clinical Principal Investigator (CPI) who is an experienced principal physiotherapist. The **SURE** program booklet also consists of selected motor tasks to be performed by the subjects using their affected UL. Functional activities such as subjects will be using their affected UL to wipe their faces; wiping the table after eating; applying lotion by the affected hand along the unaffected arm and legs after shower; drinking water from cup/ bottle; lifting and placing affected hand on table top; etc. Each functional motor task will be selected, graded and progressed by the PI according to the subjects' affected UL motor capability during the reviews. The subjects will be taught how to perform the exercises and functional tasks during the first session. The performance of the exercises and functional motor tasks will be reviewed by the CPI three times per week for the first 2 weeks, two times for the third week and one time for the fourth week of intervention period.

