6. METHODS AND ASSESSMENTS

Outcome Measures

UL functional outcome measures

UL Fugl Meyer Scale (ULFM)

UL Fugl Meyer Scale will be used to stratify subjects to their level of UL severity and assessment of UL impairment. ULFM score can be subdivided into 3 categories to define the different level of severity of paresis (severe= 0 to 22; moderate=23 to 50; mild>= 51). ULFM will be one of the primary outcome measures to determine UL recovery.

Action Research Arm Test (ARAT)

ARAT will be used as the primary outcome measure of UL functional outcome. ARAT will be one of the primary outcome measures to determine UL recovery.

Measure of UL practice and use

Rating of Everyday Arm-use in the Community and Home (REACH Scale)

The REACH scale is a self-report measure that captures how much an individual with stroke use affected UL outside clinical setting. It has one scale for subjects whose dominant UL is affected and another scale for subjects whose non-dominant UL is affected. It will be used to rate patients' affected UL use after discharge.

Measure of UL practice and use using accelerometry

One tri-axial accelerometer (ActiGraph GT3X+, ActiGraph LLC, Pensacola, Florida) will be placed on subject's unaffected wrist to establish the duration of unaffected UL use in the ward for 3 days in the first week. Another tri-axial accelerometer will be placed on subject's affected wrist for 3 weekdays each week of the 4-week intervention period to assess the amount of affected UL use. The accelerometers will be worn by all subjects (both experimental and control groups) from 8am to 8 pm on the day of donning.

Measures of feasibility of accelerometry in measuring affected UL use

The compliance rate of wearing the accelerometers during the 4 weeks of intervention period will be used to assess compliance. Subjects will also be asked to fill a questionnaire to rate the acceptance, ease, comfort, discomfort, benefits, and problems of wearing the accelerometers in the ward.

*Measures of **SURE** program's feasibility*

The key measure of **SURE** program's feasibility will be the additional affected UL practice and use per day as measured by the accelerometers.

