6.1. Randomisation and Blinding

Random assignment of subjects will be done using the randomizer found in the web (www.Randomizer.org/form.htm). A non-team member will generate the randomized allocation sequence, seal the group numbers in individual envelopes, and arrange them according to the randomized allocated sequence. These envelopes will be kept under lock and key in TTSRHC. The same non-team member will pass these sealed envelopes in accordance to the randomized allocated sequence one at a time to the CPI who will enrol and assign the eligible subjects to their groups. The unmasking of the randomization will be at the end of data collection and fMRI analysis. A blinded assessor will perform all the clinical assessments. The I2R who will be performing the fMRI analysis will be blinded to the group which the subjects are in.

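### Section 11.2 compares two unmatched randomised groups on the primary outcomes with the Wilcoxon signed-rank test, a paired test; the rank-sum test fits the design

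*Protocol*

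**What the plan says.** Section 11.2 (Analysis of UL Functional Outcome) states: "Wilcoxon signed-ranked tests will be used at each time points". It lists five time points, from pre-intervention to three months post-intervention, and gives the purpose as "to compare UL functional outcomes between the experimental and control groups". All tests use p<0.05, and the same paragraph adds: "All data will be analysed by intention to treat".

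The outcomes concerned are ULFM and ARAT. Section 6 calls each of them primary; for ARAT it says "ARAT will be one of the primary outcome measures to determine UL recovery".

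Sections 3.1, 5 and 5.1 describe random assignment of 20 subjects, 10 to each group. Section 6.1 describes the mechanism: "A non-team member will generate the randomized allocation sequence, seal the group numbers in individual envelopes". Neither there nor elsewhere is a subject in one group matched to a subject in the other.

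Later in Section 11.2, under the feasibility analysis, the same test returns for a different purpose: "Wilcoxon signed-rank test will also be used to compare outcomes of pain, fatigue and spasticity", there before versus after the intervention.

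**The concern.** The signed-rank test takes one difference per matched pair, ranks the absolute differences, and sums the ranks of those with a given sign. It needs a rule that says which observation goes with which. Before and after values of one subject supply that rule. Two independently randomised groups do not.

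Two things are at stake. First, the p-value for the primary outcomes is not a function of the data alone, because it also depends on a pairing the protocol never defines. Two analysts who both follow the text could reach different verdicts, and a pairing could be chosen after the data are seen. Second, the test uses complete pairs only. Whenever the groups observed at a visit differ in size, the surplus subjects drop out of the comparison although their data exist, contrary to the intention-to-treat statement.

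**Working it through.** **Is there a pairing anywhere?** Section 6 says ULFM will be used to stratify subjects by severity. Strata are groups of similar subjects and do not define one-to-one partners. The sealed-envelope sequence in Section 6.1 allocates single subjects. The rank-sum (Mann-Whitney) test is not named anywhere in the protocol.

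**Could the sentence mean a within-subject test?** It lists visits, but the contrast it states is between groups. The later pain, fatigue and spasticity analysis is the within-subject one, and there the test fits.

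**Inputs.** From the protocol: 10 per group and a significance level of 0.05. Assumed, because the protocol gives no effect size, SD, dropout rate or sidedness: two-sided tests, independent normal outcomes with equal SD, true differences of 0 to 2 SD, pairing blind to outcome, and the unequal group sizes below. Section 11.1 sets the sample size by feasibility, so there is no power figure to reproduce.

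**Formulas.**
- Signed-rank: with d_i = x_i − y_π(i), W+ is the sum of the ranks of |d_i| over pairs with d_i > 0. The pairing π is undefined. At 10 v 10 there are 10! = 3,628,800 possible choices.
- Rank-sum: U is the number of (i, j) with x_i > y_j, over all 10 × 10 = 100 cross-group comparisons. No pairing enters, so each data set gives one p-value.

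**Exact type I error at 10 v 10.**
- Signed-rank with 10 pairs rejects at W ≤ 8: 2 × 25/1024 = 4.9%.
- Rank-sum rejects at U ≤ 23: 4.3%.

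Neither exceeds 5%.

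**Dependence on the pairing.** Share of simulated 10 v 10 trials in which two random pairings of the same data disagree at p<0.05 (100,000 trials per row):

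| True difference (SD) | Disagree |
|---|---|
| 0 | 4% |
| 0.5 | 10% |
| 1.0 | 17% |
| 1.3 | 15% |
| 1.5 | 11% |
| 2.0 | 3% |

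Two single data sets show the spread. In one built from evenly spaced normal scores with a shift of 1.0 SD, the rank-sum test gives p = 0.043, while the signed-rank test gives p<0.05 in 44% of pairings (central 95% of p-values 0.006 to 0.19). That case sits at the threshold by construction; with shifts of 0.5 and 1.5 SD the shares are 1% and 99%. In a second, simulated set with a clear difference, all 5,000 pairings tried gave p between 0.005 and 0.013. The choice of pairing therefore matters mainly when the result is near 0.05.

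**Power at a true difference of 1.3 SD.** This is close to the difference detectable with 80% power at 10 per group under the normal approximation, (1.960 + 0.842) × √(2/10) = 1.25 SD.

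| Observed in the two groups | Rank-sum | Signed-rank (pairs used) |
|---|---|---|
| 10 v 10 | 74% | 72% (10) |
| 11 v 10 | 76% | 72% (10) |
| 10 v 9 | 71% | 61% (9) |
| 10 v 8 | 68% | 54% (8) |
| 10 v 7 | 64% | 50% (7) |

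Part of the drop at 9 and 8 pairs is discreteness and not lost subjects. The attainable level of the signed-rank test is 2 × 10/512 = 3.9% with 9 pairs and 2 × 5/256 = 3.9% with 8, against 4.9% with 10.

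**Can the groups become unequal?** Section 3.5 says: "Subject will be withdrawn from the study if the subject is unable to tolerate the SURE program". Only the experimental group receives SURE, so this rule acts on one group. Section 3.6 replaces dropouts, so a single replacement makes 21 randomised subjects, an odd number that cannot be fully paired. Section 6.3e says no effort will be made to follow up subjects who withdraw from the program unless they ask. Unequal numbers at a visit are therefore possible. How often they would occur cannot be derived from the protocol.

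**The case against.** The strongest reply is that this is a slip of the pen for the other Wilcoxon test, in a 20-subject exploratory pilot with no power claim. Any competent analyst would notice it. At the planned 10 v 10 nobody is lost, type I error holds and power changes by about 2 points. Losses arise only if the groups become unequal, no dropout rate is given, and replacement is meant to offset dropout. A withdrawn subject with no later data is missing under either test, so changing the test does not repair that part of the intention-to-treat problem. Finally, the simulations assume continuous normal data, whereas ULFM is scored in whole numbers and produces ties.

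Most of this stands as a limit on the consequences. Loss of subjects is conditional on unequal groups, and only observed subjects without a partner are recovered by the change. The 44% example is a threshold case; the averages of 3% to 17% are the fairer summary.

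It does not rescue the sentence. A slip is the likely explanation, but the protocol names the same test again for the truly paired analysis and says it will also be used there, so a reader cannot tell that a different test was meant. A separate analysis plan would have to contradict the protocol or repeat the error.

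**Conclusion.** The concern holds. The only test named for ULFM and ARAT requires pairs that the design does not contain, so it cannot be carried out without an invented step that can change the verdict. Under the stated normal, equal-SD assumptions, two arbitrary pairings disagree in 3% to 17% of trials, depending on the true difference. Where the observed groups are unequal, the assumed cases at 1.3 SD show power losses of 4 points (11 v 10) to 14 points (10 v 8 and 10 v 7). There is no inflation of type I error if the pairing is made without sight of the outcomes, and at 10 v 10 the power loss is small. The correction is needed because the primary analysis is undefined as written, not because of a large loss of efficiency.

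**What to change.** In Section 11.2, under the analysis of UL functional outcome, name the Wilcoxon rank-sum (Mann-Whitney) test for the comparison between the experimental and control groups. Keep the signed-rank test for the pre- versus post-intervention comparisons of pain, fatigue and spasticity. This gives one p-value per outcome and visit and uses every observed subject. Adjustment for baseline at later visits, or a group difference with a confidence interval, would be useful but is optional.

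The cost is one test name in one sentence. No extra subjects, visits or data are needed.

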The subjects will be asked to perform the exercises 60 minutes (3x 10- 20 minutes) distributed across morning, afternoon, and evening per day for 6 days per week during the 4-week intervention period. They will also be asked to perform the functional tasks as and when is required for their daily function for 6 days per week during the 4-week intervention period. The subjects will be given an Exercise Log to tick and track number of repetitions of the exercises and functional activities each day, the number of days the protocol is completed, and the level of fatigue and pain experienced. If the subject is discharged from the hospital before the 4 weeks of intervention period, he/ she has to carry on with the protocol till the intervention period ends. The CPI will continue to review exercises and the amount of affected UL use with the subjects at home if the subjects are discharged till the intervention period ends.

Control Group

The control group will receive an education booklet with 10 modules. The education booklet will contain information on stroke, recovery and management strategies after stroke. Subjects are to complete 2-3 modules per week and answer 1-2 simple questions after each module. Each module including answering questions takes approximately 5-10 minutes to complete. The CPI will review the information with the subjects 3 times per week for the first 2 weeks, two times for the third week and one time for the fourth week of intervention period.

Both groups will continue with their daily routine therapy sessions in the hospital. The treating therapists will record the duration of therapy of each subject per day.

UL functional outcome measures- ULM and ARAT will be assessed pre-intervention, 2 weeks after start of intervention, post-intervention, 1month and 3months post-intervention. Measures of **SURE** program's feasibility such as VAS pain score, fatigue level, and MAS of biceps and finger flexors will be measured pre-intervention, 2 weeks after start of intervention and post-intervention. A team member who is blinded to which group the subjects are in will perform the outcome measure assessments.

Multimodal imaging for the normal healthy control will be performed once to establish the activation pattern in normal. Multimodal imaging assessment for the patient subjects will be done pre-intervention, post-intervention, and 3months post-intervention.

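### Two primary arm scales are each tested between groups at four post-baseline visits at p<0.05, and no scale or visit is named as the one that answers the effectiveness objective

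*Protocol*

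**What the plan says.** Section 2.2 gives, as part of the primary objective, the effectiveness of SURE in improving upper-limb functional outcomes. Section 2.1 states the same as the first hypothesis.

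Section 5 identifies those outcomes: "UL functional outcome measures- ULM and ARAT will be assessed pre-intervention", and at four later visits (ULM there is evidently ULFM).

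Section 6 gives both scales primary status. For the Fugl-Meyer: "ULFM will be one of the primary outcome measures to determine UL recovery". For ARAT, two consecutive sentences: "ARAT will be used as the primary outcome measure of UL functional outcome" and "ARAT will be one of the primary outcome measures to determine UL recovery".

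Section 11.2 then sets the analysis: "Wilcoxon signed-ranked tests will be used at each time points (pre, 2 weeks after start of intervention, post, 1month post-intervention, 3months post-intervention"), in order "to compare UL functional outcomes between the experimental and control groups". The threshold follows: "The significance level for all statistical tests will be set at" p<0.05.

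Section 11.1 describes the study as an exploratory pilot. It sets 10 per group by what can be recruited in the two-year funding period and gives no effect size or power.

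The only measure against multiple testing concerns MRS, where Section 11.2 restricts the analysis to GABA and Glx. Nothing comparable is said for ULFM and ARAT.

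**The concern.** The protocol fixes one significance level for every test, applies it to two primary scales at several visits, and does not say which comparison answers the primary question. A reader of the results could not tell whether a significant ARAT difference at two weeks, or a significant ULFM difference at three months, is the answer to the objective or one of several looks. The scale and visit could be chosen after the data are seen.

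With 10 per group and no power basis, an isolated significant result is weak evidence. The error rate that a reader would attach to it (5%) would not be the rate of the procedure that produced it.

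**Working it through.** The protocol states no family-wise error rate and no power, so there is no figure of its own to reproduce.

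**Inputs from the protocol**
- Scales: 2, ULFM and ARAT (Sections 5 and 6).
- Visits tested: 5 (Section 11.2), of which 1 precedes the intervention, leaving 4.
- Level: 0.05 per test, no adjustment (Section 11.2). Sidedness is not stated; two-sided is assumed.
- Group size: 10 and 10 (Sections 3.1 and 11.1).

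**Assumptions**
- Correlations between visits and between scales are not given. A range of 0.6 to 0.95 is used, with independence as a benchmark.
- The exact two-sided rank-sum test replaces the signed-rank test of Section 11.2. The signed-rank test is for paired data, and the two groups are independent.

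**Step 1. Size of the family.** A difference before the intervention cannot be evidence that SURE works, so the baseline tests are left out: 2 × 4 = 8 tests.

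**Step 2. Size of one test.** For 10 v 10 the exact rank-sum test rejects when U ≤ 23 or U ≥ 77. Its true two-sided size is 0.0433, or 0.0433 / 2 ≈ 0.0216 in the direction of SURE.

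**Step 3. Independence benchmark.**
- Two-sided, exact size: 1 − (1 − 0.0433)^8 ≈ 0.298.
- Two-sided, nominal 0.05: 1 − 0.95^8 = 0.337.
- In favour of SURE, exact size: 1 − (1 − 0.0216)^8 ≈ 0.160.

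**Step 4. Correlated tests.** Trials were simulated with no effect on either scale at any visit: multivariate normal data, equal correlation among visits, 40,000 trials per setting.

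| Correlation, visits / scales | Any false result in 8 tests, two-sided | Any false result in favour of SURE |
|---|---|---|
| 0.6 / 0.7 | 22% | 11% |
| 0.8 / 0.8 | 17% | 8% |
| 0.9 / 0.9 | 13% | 6% |
| 0.95 / 0.95 | 10% | 5% |
| Independent | 30% | 16% |
| One test only | 4.3% | 2.2% |

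**Step 5. Would settling the scale alone be enough?** If ARAT were the only primary scale, its four post-baseline visits would still give about 8 to 13% two-sided over the same range of correlations. The visit has to be named as well.

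**The case against.** **The protocol may leave this to an SAP.** A hierarchy and the handling of multiple tests are often set there, and an SAP may exist. A general level of 0.05 does not by itself exclude a hierarchy. This stands in part. But the protocol is not merely silent: it gives two scales primary status, lists the visits to be tested and sets the level for all tests.

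**It is a pilot.** Control of the family-wise error is mainly a requirement of confirmatory trials. This lowers the stakes. However, Section 11.1 uses the label to explain the sample size and the individual-level study of neuroplasticity. Sections 2.1, 2.2 and 11.2 keep the effectiveness hypothesis, the objective and the significance tests.

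**The two-sided rate overstates the harm.** Only an error in favour of SURE would be an overclaim. That is fair, which is why the table shows both. At correlation 0.95 the favourable rate is about 5%, so it is not well above 5% in absolute terms. It is still more than twice the 2.2% of a single test.

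**Stronger readings that the text does not support.**
- A reader might infer that one significant result out of several is to count as proof of effectiveness. The protocol contains no such rule. The rates above describe what that reading would cost, not a stated decision rule.
- A reader might count ten tests by including baseline. Section 11.2 does plan baseline tests, but they cannot produce an effectiveness claim.
- A reader might see a contradiction in ARAT being called both the primary measure and one of the primary measures. The sentences can be reconciled: ARAT as the primary measure of function, and both scales as primary for recovery. The wording is loose, not clearly contradictory.
- A reader might call this the likeliest route to an overclaim in this trial. Nothing in the protocol ranks it against other routes, such as the paired test or the quarterly interim analysis.

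**Conclusion.** The concern holds in a limited form. Eight post-baseline between-group tests on two primary scales are each set at 0.05, and none is identified as answering the effectiveness objective. Following that plan, the chance of at least one false two-sided result is about 10 to 22% for correlations between 0.95 and 0.6, with 30% as the independent case. For a false result favouring SURE it is about 5 to 11%, roughly two to five times the 2.2% of one test.

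The size rests on assumed correlations, normally distributed scores without ties, and the exact rank-sum test in place of the test that is named. The direction does not depend on the exact values: any correlation short of 1 leaves the rate above that of a single test. Because the trial is an exploratory pilot, this is a correction that should be made, not a flaw that invalidates the design.

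**What to change.** In Sections 6 and 11.2, name one scale at one visit as the primary comparison, tested at p<0.05. ARAT at the post-intervention visit is one candidate, since Section 6 already singles it out for function; the sponsor may choose another. Report the other scale and the other post-baseline visits as between-group differences with 95% confidence intervals, labelled exploratory and without an effectiveness claim. Replace the pre-intervention significance test with a descriptive comparison of the groups at baseline.

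If the sponsor wants both scales as primary at one visit, testing each at 0.05 / 2 = 0.025 keeps the overall rate at or below 0.05. Keeping all eight tests as primary would need 0.05 / 8 = 0.00625 each, which is severe with 10 per group.

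The change takes a few sentences and needs no further subjects, visits or data. The price is that the sponsor can no longer claim effectiveness from the other scale, or from a follow-up visit, alone.

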5.1. Summary of Study Design

The subjects will be randomly assigned to a control (N=10) and experimental group (N=10). The control group will undergo an education program while the experimental group will undergo the **SURE** program. Clinical assessments for both groups will be performed by a blinded assessor at pre, two weeks after start of intervention, immediate post intervention, 1 and 3months post-intervention to determine if the **SURE** program improve affected UL functional outcomes compared with the control group. fMRI investigations will be performed at pre-intervention, post- intervention and 3months post-intervention to determine if the increased UL activity in the **SURE** program influences brain neuroplasticity positively early post-stroke.

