On the day of travel, the CPI will check with the treating doctor if the subject is clinical fit to travel, if the doctor deems the subject clinically unfit to travel, the ambulance services and TMS/ fMRI will be cancelled for that day and the subject will remain in the ward and not travel. If the doctor deems the subject clinically stable to travel, the subject will be accompanied by CPI and paramedic in the ambulance service to NUH and CIRC.

In the process of transportation, if the subject suffers any adverse events or re-stroke, the paramedic accompanying the subject in the ambulance will manage the emergency situations and send the subject to the nearest hospital Emergency Department. The CPI will call the treating doctor in TTSHRC to inform and update on the emergency situation and subject's location. The CPI will stay with the subject until further instructions has been given by the treating doctor in TTSHRC.

c. *Final Study Visit:*

The final study visit will be either the three-months post-intervention clinical assessment or fMRI investigation.

d. *Post Study Follow up and Procedures*

CPI will check on all clinical assessments and TPI will check on all fMRI investigations to ensure that all the assessments and investigations are done accurately and the results obtained are accurately. CPI and TPI will also check and monitor for any adverse events occurring during **SURE** program and fMRI investigations.

e. *Discontinuation Visit and Procedures*

All clinical assessments and fMRI investigations should be done until the subject indicate to the CPI that he/she want to withdraw voluntarily from participation in the study at any time. Subjects may also withdraw voluntarily from receiving the **SURE** program for any reason. All the withdrawals and reasons for withdrawal will be evaluated to gain an insight to the feasibility of SURE program. As **SURE** program is a safe exercise program, no efforts will be made to follow-up if the subject chooses to withdraw from the program, unless subject has specifically requested for follow-up.

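### Section 3.5 takes subjects who cannot tolerate SURE out of the study, section 6.3e keeps assessing them; following 3.5 loses outcomes in the SURE arm only and undermines the intention-to-treat analysis

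*Protocol*

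**What the plan says.** The relevant protocol text is in five places.

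- **Section 11.2**, on the upper-limb functional outcomes: "All data will be analysed by intention to treat".
- **Section 3.5**, the only withdrawal criterion: "Subject will be withdrawn from the study if the subject is unable to tolerate the SURE program".
- **Section 6.3e**: "All clinical assessments and fMRI investigations should be done until the subject indicate to the CPI that he/she want to withdraw voluntarily from participation". It then treats leaving the exercises as something different: "Subjects may also withdraw voluntarily from receiving the" SURE program. It adds that "no efforts will be made to follow-up if the subject chooses to withdraw from the program", unless the subject asks for it. It does not say whether this means outcome visits or safety follow-up.
- **Section 5.1**, on who is exposed to what: "The control group will undergo an education program while the experimental group will undergo the" SURE program.
- **Section 5**, on the schedule: "UL functional outcome measures- ULM and ARAT will be assessed pre-intervention, 2 weeks after start of intervention, post-intervention, 1month and 3months post-intervention". Imaging is done before and after the intervention and three months later.

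Section 3.6 adds that dropouts are replaced.

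**The concern.** Sections 3.5 and 6.3e give different instructions for the same subject, and neither is said to prevail. Under 3.5 a subject who cannot tolerate the exercises leaves the study. Under 6.3e that subject is still assessed until he or she chooses to leave. Two staff members could treat the same case differently and both be following the protocol.

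The 3.5 route is open in one arm only and is triggered by the treatment. If it is followed, the remaining SURE subjects are those who tolerated the program, and they are compared with all controls, including those who would not have tolerated it. That comparison no longer has the protection of randomisation, whatever the analysis is called. It affects the Fugl-Meyer, ARAT and imaging comparisons.

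The tolerability data suffer too. Section 11.2 will "compare outcomes of pain, fatigue and spasticity pre-and post-intervention period". Section 2.4b names persistent fatigue as a reason to reconsider whether a subject continues SURE, so the missing post-intervention scores may be those of the subjects who were most fatigued.

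**Working it through.** **Text comparison**

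| Question | Section 3.5 | Section 6.3e |
|---|---|---|
| What ends participation? | Inability to tolerate SURE | The subject's own decision to leave the study |
| Is stopping SURE separate from leaving the study? | No | Yes |
| Do assessments continue after SURE stops? | No, on the natural reading of withdrawal from the study | Yes, under the first sentence; the later follow-up sentence leaves this unclear |
| Which arm can be affected? | SURE only | Voluntary withdrawal from the study: either arm |

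**Data at stake per subject**

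There are 10 subjects per arm (section 3.1). The post-baseline clinical assessments are at 2 weeks, post-intervention, 1 month and 3 months, so 10 × 4 = 40 per arm. Post-baseline scans are post-intervention and at 3 months, so 10 × 2 = 20 per arm. A subject withdrawn before the 2-week visit costs 4 of the 40 and 2 of the 20. Each such subject is 1/10 = 10% of the SURE arm; the rule removes none of the controls.

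**Illustration of the bias**

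The sample size rests on feasibility (section 11.1), so there is no planned power figure to reproduce. The protocol gives no intolerance rate and no link between intolerance and recovery; the values below are assumptions.

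Setup: no true effect. In both arms a share p would be intolerant of SURE, with outcome distributed N(−d, 1); the others are N(0, 1). All 10 controls are kept and intolerant SURE subjects are lost without replacement. The between-group test is taken to be the two-sample rank-sum with exact two-sided 5% critical values: U ≤ 23, 20, 17, 14 for 10, 9, 8, 7 subjects against 10, each with true size about 4.3%.

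- Control mean = p × (−d) + (1 − p) × 0 = −pd
- Mean of retained SURE subjects = 0
- Bias = 0 − (−pd) = **+pd** in within-group SD
- Population SD = √(1 + p(1 − p)d²)

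| p | d | Bias, within-group SD | Population SD | Bias, population SD | Rejection, two-sided | of which favouring SURE |
|---|---|---|---|---|---|---|
| no loss | – | 0.00 | – | 0.00 | 4.3% | 2.2% |
| 0.10 | 0.5 | 0.10 × 0.5 = +0.05 | √1.0225 = 1.011 | +0.05 | 4.4% | 2.7% |
| 0.20 | 1.0 | 0.20 × 1.0 = +0.20 | √1.16 = 1.077 | +0.19 | 5.6% | 4.7% |
| 0.30 | 1.5 | 0.30 × 1.5 = +0.45 | √1.4725 = 1.213 | +0.37 | 9.1% | 8.8% |

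If the intolerant 20% recover 1 SD better, the bias is −0.20 within-group SD (−0.19 population SD). If everyone is assessed and kept in the allocated arm, the bias is 0.00 and rejection stays at 4.3% to 4.4%.

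**Effect of replacement (section 3.6).** If every withdrawn subject is replaced until 10 tolerant subjects are in the SURE arm, the retained mean is still 0, so the bias is still pd. Because the arm is back to full size, rejection is slightly higher: about 4.4%, 5.8% and 11.1% in the three cases.

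**A harsher assumption.** If the subjects lost are exactly the 1, 2 or 3 with the worst outcomes in the SURE arm, rejection is about 6%, 10% or 16%. Nothing in the protocol supports so tight a link, and the conclusion does not use it.

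**The case against.** The strongest reply is that the sections describe two routes: 3.5 a withdrawal decided by staff, 6.3e a withdrawal chosen by the subject. Section 2.4b also handles persistent fatigue at program level, so staff might stop the exercises and go on assessing. This does not remove the conflict. Section 6.3e continues assessments until voluntary withdrawal and makes no exception for 3.5. And if the routes are separate, the 3.5 route still removes subjects from one arm.

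Four further points have some force:

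- **Lost visits are inferred.** Section 3.5 does not say outright that assessments stop. That is fair, although it is the natural reading. The no-follow-up sentence in 6.3e is justified there by the safety of the exercises, so it may mean safety follow-up only; I do not count it as a second source of loss.
- **Intention to treat concerns analysis by allocated group.** Missing visits do not contradict that sentence literally, and handling of missing data can be left to the analysis plan. This stands as a point of wording: the promise is undermined, not broken. But no analysis plan can restore visits that were never held.
- **Size.** The low and middle cases are small. Graded exercises and rest advice may make intolerance uncommon. Withdrawals are evaluated and the dropout rate is reported, so the loss would be visible.
- **Pilot status.** With 10 per arm chosen for feasibility, no p-value carries much weight. Effectiveness is nonetheless a primary objective (section 2.2) and is tested at 0.05.

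**Conclusion.** The concern holds. Sections 3.5 and 6.3e cannot both be followed as written for a subject who cannot tolerate SURE and has not asked to leave, and the 3.5 trigger exists in the experimental arm only. Following 3.5 costs up to 4 clinical assessments and 2 scans per subject, for a treatment-related reason, and the loss is irrecoverable.

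The text conflict is established; the amount and direction of bias are not. Across the assumed cases with poorer recovery in the intolerant, the bias runs from +0.05 to +0.45 within-group SD and rejection from 4.4% to 9.1%. The sign reverses if they recover better. If intolerance is unrelated to recovery, only precision is lost. The result also assumes a two-sample rank-sum test and that assessments stop on withdrawal under 3.5. This should be fixed because the remedy is cheap and the lost data cannot be recovered, not because a material distortion has been shown.

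**What to change.** Reconcile sections 3.5, 6.3e and 11.2 on data collection:

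1. State that stopping SURE, or the education program, is separate from leaving the study.
2. State that a subject who stops stays in the allocated arm and is assessed at the remaining scheduled visits unless consent for assessment is withdrawn. Keep the existing fitness-to-travel checks before scans.
3. In 6.3e, say whether follow-up means outcome assessment or safety follow-up.

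As an optional clarification, section 3.6 could say that a replacement is an additional subject taking the next envelope, and that the subject replaced remains in the intention-to-treat set and in the denominator of the dropout rate. This may equally be left to the analysis plan.

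None of this changes the clinical decision on when a subject stops the exercises. The cost is a few sentences of protocol wording, plus visits that are already scheduled for the few subjects who stop.
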